## **1 Introduction**

This statistical analysis plan (SAP) describes all planned analyses for the clinical study report(s) (CSR) of study CETB115G2201, a non-randomized, open label, multi-center, Phase II study to assess the safety and efficacy of eltrombopag in combination with rabbit anti-thymocyte globulin (r-ATG) and cyclosporine A (CsA) in East-Asian patients with treatment naive severe aplastic anemia (SAA)

[figure not shown]
As specified in Section 12 of the study protocol (version 03 dated 22-Dec-2021), the primary analysis will be performed after all patients have completed Week 26 or discontinued prior to Week 26. Furthermore, a final analysis will be performed at the end of the study. This SAP will also support the final analysis.

The content of this SAP is based on protocol CETB115G2201 version 03 (dated 22-Dec-2021). All decisions regarding analysis, as defined in the SAP document, should be made prior to database lock.

### **1.1 Study design**

This is a non-randomized, open label, single arm, multi-center, Phase II study to evaluate the efficacy and safety of eltrombopag in combination with IST regimen of r-ATG + CsA in East-Asian patients with SAA who have not received prior IST. At least 36 subjects will be enrolled from China, Japan, Korea or Taiwan. At least 6 pediatric subjects will be recruited in total, with 3 subjects from China and 3 from Japan respectively. At least one of the 6 pediatric subjects in each age group (6 to 11 years old, and 12 to 17 years old) will be enrolled. For the 30 adult subjects, at least 12 subjects will be recruited from China to fulfill the requirements for pharmacokinetic (PK) profile.

**Figure 1-1 Study design**

Eligible subjects will be enrolled into the study and will receive eltrombopag (from Day 1 to Week 26) concomitantly with r-ATG (on Days 1-5) and CsA (from Day 1 to Week 26) in the core treatment part.

Efficacy assessments will be performed at Week 13 and Week 26 in the core treatment part of the study.

Participants who are assessed as responders (meeting CR or PR criteria) at Week 26 are eligible to the extension part of the study and continue treatment with eltrombopag and CsA after Week 26.

Study treatment should be discontinued if the participant is not assessed as a responder at Week 26.

During the extension part, eltrombopag treatment will be provided up to Week 52. CsA will be maintained or tapered at the investigator's discretion according to local practice, with a total duration of at least 2 years (18 months after Week 26).

End of treatment assessments will be performed after eltrombopag discontinuation anytime during the study. After that, safety follow-up visit will be performed 30 days after the discontinuation of eltrombopag, and participants will enter the long-term follow-up part, with yearly efficacy and clonal evolution assessments up to Year 3 (Week 156).

For non-responders at Week 26, and participants who relapse or receive alternative SAA treatment, safety follow-up visit will be performed 30 days after the discontinuation of eltrombopag, and then clonal evolution and survival will continue to be followed up to Year 3 (Week 156).

Participants who prematurely discontinue eltrombopag will have efficacy assessments at defined time points (Week 13, Week 26, Week 52 and yearly after), unless or until the occurrence of no response at Week 26, relapse or alternative SAA treatment (whichever comes first). Survival and clonal evolution data will be collected for all participants up to Year 3 (Week 156).

## 1.2 Study objectives and endpoints

For the definition of response, partial response (PR), CR, transfusion independence, and relapse, refer to [Section 2.5](#) and [Section 2.7](#).

**Table 1-1 Objectives and related endpoints**

Objective(s)	Endpoint(s)
Primary objective(s)	Endpoint(s) for primary objective(s)

To evaluate the efficacy of eltrombopag in combination with r-ATG and CsA in terms of complete response rate at 6 months in East-Asian patients with treatment naive severe aplastic anemia (SAA)

	

CR rate at Week 26 (6 months) after starting the study treatment

Secondary objective(s)	Endpoint(s) for secondary objective(s)

To evaluate complete response rate at 3, 12 months and yearly after

To evaluate overall response rate at 3, 6, 12 months and yearly after

To evaluate duration of response

To evaluate overall survival (OS)

	

CR rate at Week 13 (3 months), Week 52 (12 months) and yearly after

Overall response (CR+PR) rate at Week 13 (3 months), Week 26 (6 months), Week 52 (12 months) and yearly after

Time from the date of the start of response to the date of relapse or death, whichever occurs first at any time during the study

Time from the date of first dose of study treatment to the date of death

Objective(s)	Endpoint(s)
	

Overall survival rate at Week 26, Week 52 and yearly after

To evaluate the need for transfusion (packed RBC units and platelet units)

	

Time from the most recent transfusion to Week 13 and Week 26

Proportion of subjects who becomes (platelet/RBC) transfusion independent

To evaluate safety and tolerability of eltrombopag in combination with r-ATG and CsA

	

Frequency and severity of AEs, severe adverse events (SAEs), vital signs, electrocardiogram and laboratory abnormalities

To evaluate clonal evolution

	

Time from the date of first dose of study treatment to the date of first occurrence of any of the clonal evolution events



To determine the pharmacokinetics (PK) of eltrombopag in East-Asian treatment naive SAA patients

	

Plasma PK parameters and trough concentration of eltrombopag at steady state

## 2 Statistical methods

### 2.1 Data analysis general information

The primary analysis and final analysis will be conducted by Novartis. SAS version 9.4 or later software will be used to perform all data analyses and to generate tables, figures and listings.

#### Data included in the analysis

The analysis cut-off date for the primary analysis of study data will be established after all enrolled patients have completed 26 weeks of treatment or have withdrawn prior to Week 26. All statistical analyses will be performed using all data collected in the database up to the data cutoff date. All data with an assessment date or event start date (e.g. vital sign assessment date or start date of an adverse event) prior to or on the cut-off date will be included in the analysis. Any data collected beyond the cut-off date will not be included in the analysis and will not be used for any derivations.

All events with start date before or on the cut-off date and end date after the cut-off date will be reported as 'ongoing'. The same rule will be applied to events starting before or on the cut-off date and not having documented end date. This approach applies, in particular, to adverse event, concomitant medication reports and exposure to eltrombopag. For these events, the end date will not be imputed and therefore will not appear in the listings.

The analysis cutoff date for the final analysis of study data will be established at the end of the study.

## **General analysis conventions**

**Pooling of centers:** Unless specified otherwise, data from all study centers will be pooled for the analysis. Due to expected small number of patients enrolled at centers, no center effect will be assessed.

**Qualitative data** (e.g., gender, race, etc.) will be summarized by means of contingency tables; a missing category will be included as applicable. Percentages will be calculated using the number of patients in the relevant population or subgroup as the denominator.

**Quantitative data** (e.g., age, body weight, etc.) will be summarized by appropriate descriptive statistics (i.e. mean, standard deviation, median, minimum, and maximum and first and third quartiles when appropriate). PK parameters except Tmax will be summarized by appropriate descriptive statistics (n, arithmetic mean, CV% mean, standard deviation (SD), median, geometric mean, CV% geo-mean, minimum and maximum).

### **2.1.1 General definitions**

#### **Investigational drug**

The investigational drug for this study is eltrombopag (ETB115).

#### **Study treatment**

Study treatment includes any of the following: r-ATG, CsA, eltrombopag or combination of these drugs administered to the patient as part of the required study procedures up to the end of Year 2.

#### **Date of first administration of investigational drug**

The date of first administration of investigational drug is defined as the first date when a non-zero dose of investigational drug (eltrombopag) is administered and recorded on the Dosage Administration Record (DAR) eCRF. The date of first administration of investigational drug will also be referred to as start of investigational drug.

#### **Date of last administration of investigational drug**

The date of last administration of investigational drug is defined as the last date when a nonzero dose of investigational drug (eltrombopag) is administered and recorded on the DAR eCRF. The date of last administration of investigational drug will also be referred to as end of investigational drug.

#### **Date of first administration of study treatment**

The date of first administration of study treatment is derived as the first date when a nonzero dose of any component of study treatment was administered as per the DAR eCRF. (Example: if 1st dose of eltrombopag is administered on 05-Jan-2015, and 1st dose of combination partner is administered on 03-Jan-2015, then the date of first administration of study treatment is 03-Jan-2015).

### **Date of last administration of study treatment**

The date of last administration of study treatment is derived as the last date when a nonzero dose of any component of study treatment was administered as per the DAR eCRF. (Example: if the last eltrombopag dose is administered on 15-Apr-2014, and the last dose of a combination partner is administered on 17-Apr-2014, then the date of last administration of study treatment is 17-Apr-2014).

### **Study day**

The study day, describes the day of the event or assessment date, relative to the reference start date.

The study day is defined as:

- The date of the event (visit date, onset date of an event, assessment date etc.) – reference start date + 1 if event is on or after the reference start date;
- The date of the event (visit date, onset date of an event, assessment date etc.) – reference start date if event precedes the reference start date.

The reference date for all assessments (safety, efficacy, pk, etc) is the start of study treatment.

The study day will be displayed in the data listings. If an event starts before the reference start date, the study day displayed on the listing will be negative.

### **Time unit**

A year length is defined as 365.25 days. A month length is 30.4375 days (365.25/12). If duration is reported in months, duration in days will be divided by 30.4375. If duration is reported in years, duration in days will be divided by 365.25.

### **Baseline**

For safety and efficacy evaluations, the last available assessment on or before the date of start of study treatment is defined as “baseline” assessment.

For ECG assessment, the average of the triplicate assessment should be used as baseline.

If patients have no value as defined above, the baseline result will be missing.

### **On-treatment assessment/event and observation periods**

For adverse event reporting the overall observation period will be divided into three mutually exclusive segments:

1. ***pre-treatment period***: from day of patient's informed consent to the day before first administration of study treatment
2. ***on-treatment period***: from date of first administration of study treatment to 30 days after date of last administration of eltrombopag.
3. ***post-treatment period***: starting at day 30+1 after last dose of eltrombopag.

Safety summaries (tables, figures) include only data from the on-treatment period with the exception of baseline data which will also be summarized where appropriate (e.g. change from baseline summaries). In addition, a separate summary for death including on treatment and post treatment deaths will be provided. In particular, summary tables for adverse events (AEs) will summarize only on-treatment events, with a start date during the on-treatment period (**treatment-emergent** AEs).

However, all safety data (including those from the post-treatment period) will be listed and those collected during the pre-treatment and post-treatment period will be flagged.

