3. its duration (start and end dates) or if the event is ongoing, an outcome of not recovered/not resolved must be reported
4. whether it constitutes a SAE (see [Section 10.1.2](#) for definition of SAE) and which seriousness criteria have been met
5. action taken regarding with study treatment

All AEs must be treated appropriately. Treatment may include one or more of the following:

- Dose not changed
- Dose Reduced/increased
- Drug interrupted/withdrawn
- Its outcome

1. not recovered/not resolved;
2. recovered/resolved;
3. recovered/resolved with sequelae;
4. fatal; or unknown.

If the event worsens, the event should be reported a second time in the CRF noting the start date when the event worsens in toxicity. For grade 3 and 4 AEs only, if improvement to a lower

grade is determined a new entry for this event should be reported in the CRF noting the start date when the event improved from having been Grade 3 or Grade 4.

Conditions that were already present at the time of informed consent should be recorded in medical history of the participant.

AEs (including lab abnormalities that constitute AEs) should be described using a diagnosis whenever possible, rather than individual underlying signs and symptoms.

AE monitoring should be continued for at least 30 days following the last dose of eltrombopag.

Once an AE is detected, it must be followed until its resolution or until it is judged to be permanent (e.g. continuing at the end of the study), and assessment must be made at each visit (or more frequently, if necessary) of any changes in severity, the suspected relationship to the interventions required to treat it, and the outcome.

Information about adverse drug reactions for the investigational drug can be found in the eltrombopag Investigator's Brochure.

Abnormal laboratory values or test results constitute AEs only if they fulfill at least one of the following criteria:

- they induce clinical signs or symptoms
- they are considered clinically significant
- they require therapy

Clinically significant abnormal laboratory values or test results must be identified through a review of values outside of normal ranges/clinically notable ranges, significant changes from baseline or the previous visit, or values which are considered to be non-typical in participants with the underlying disease.

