Summary tables for AEs will include only AEs that started or worsened during the on-treatment period, the **treatment-emergent** AEs.

The incidence of treatment-emergent AEs (new or worsening from baseline) will be summarized by system organ class and or preferred term, severity (based on CTCAE grades), type of AE, relation to study treatment.

SAEs, non-serious AEs and AESI during the on-treatment period will be tabulated.

All deaths (on-treatment and post-treatment) will be summarized.

All AEs, deaths, and SAEs (including those from the pre- and post-treatment periods) will be listed and those collected during the pre-treatment and post-treatment period will be flagged.

Vital signs

All vital signs data will be listed by participant, and visit/time and if ranges are available, abnormalities will be flagged. Summary statistics will be provided by treatment and visit/time.

12-lead ECG

PR, QRS, QT, QTcF and RR intervals will be obtained from 12-lead ECGs for each participant during the study.

Shift tables of ECG findings ('Normal' or 'Abnormal') from baseline to worst on-treatment result will be generated. Descriptive statistics at baseline, one or several post-baseline time points and change from baseline to this/these post-baseline time points will be presented.

ECG evaluations for all participants with at least 1 abnormality will be listed. All ECG data will be listed by participant and visit/time, abnormalities will be flagged.

Clinical laboratory evaluations

All laboratory data will be listed by participant and visit/time and if normal ranges are available, abnormalities will be flagged. Summary statistics will be provided by treatment and visit/time. Shift tables using CTCAE grades or the low/normal/high/ (low and high) classification will be used to compare baseline to the worst on-treatment value.

Grading of laboratory values will be assigned programmatically as per NCI Common Terminology Criteria for Adverse Events (CTCAE), version 4.03. The calculation of CTCAE grades will be based on the observed laboratory values only, clinical assessments will not be taken into account.

CTCAE Grade 0 will be assigned for all non-missing values not graded as 1 or higher. Grade 5 will not be used.

For laboratory tests where grades are not defined by CTCAE, results will be categorized as low/normal/high based on laboratory normal ranges.

The following summaries will be generated separately for hematology, and biochemistry tests:

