## **2.8 Safety analyses**

For all safety analyses, the safety set will be used. All listings and tables will be presented for all subjects.

Safety summaries (tables, figures) include only data from the on-treatment period with the exception of baseline data which will also be summarized where appropriate (e.g., change from

baseline summaries). In addition, a separate summary for death including on treatment and post treatment deaths will be provided. In particular, summary tables for AEs will summarize only on-treatment events, with a start date during the on-treatment period (treatment-emergent AEs).

The on-treatment period lasts from the date of first administration of study treatment to 30 days after the date of the last actual administration of eltrombopag.

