#### **General rules for AE Reporting**

AE summaries will include all AEs occurring during on treatment period. All AEs collected in the AE (e)CRF page will be listed along with the information collected on those AEs e.g. AE relationship to study drug, AE outcome etc. AEs with start date outside of on-treatment period will be flagged in the listings.

AEs will be summarized by number and percentage of subjects having at least one AE, having at least one AE in each primary system organ class (SOC) and for each preferred term (PT) using MedDRA coding. A subject with multiple occurrences of an AE will be counted only once in the respective AE category. A subject with multiple CTCAE grades for the same preferred term will be summarized under the maximum CTCAE grade recorded for the event. AE with missing CTCAE grade will be included in the 'All grades' column of the summary tables.

In AE summaries, the primary system organ class will be presented alphabetically and the preferred terms will be sorted within primary SOC in descending frequency. The sort order for the preferred term will be based on their frequency.

The following adverse event summaries will be produced for AEs occurring during the on-treatment period; overview of adverse events and deaths, AEs by SOC and PT, summarized by maximum CTCAE grade, summarized by relationship (all AEs and AEs related to eltrombopag/CsA/r-ATG), seriousness (SAEs and non-SAEs), leading to treatment discontinuation, leading to dose interruption/changes, requiring additional therapy and leading to fatal outcome. Specifically, CTC grade  $\geq 3$  adverse events will be summarized for AEs by SOC and PT.

Furthermore, AE occurring during the on-treatment period will be summarized by subgroup summarized by the above subgroups listed in [section 2.2.1](#). These summaries include: AEs by SOC and PT, AEs with suspected relationship to eltrombopag by SOC and PT and SAEs by SOC and PT.

In addition, on treatment adverse events will be summarized by SOC and PT and by periods (by  $\leq 30$  days,  $>30$  to  $\leq 90$  days,  $>90$  to  $\leq 180$  days,  $>180$  to  $\leq 360$  days). Time of onset of first episode will be used when experiencing the same episode in a subject.

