## **2.8 Safety analyses**

For all safety analyses, the safety set will be used. All listings and tables will be presented for all subjects.

Safety summaries (tables, figures) include only data from the on-treatment period with the exception of baseline data which will also be summarized where appropriate (e.g., change from baseline summaries). In addition, a separate summary for death including on treatment and post treatment deaths will be provided. In particular, summary tables for AEs will summarize only on-treatment events, with a start date during the on-treatment period (treatment-emergent AEs).

The on-treatment period lasts from the date of first administration of study treatment to 30 days after the date of the last actual administration of eltrombopag.

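### The SAPs' start-date rule counts a pre-dose Grade 3-4 event that improves after Day 1 as treatment-emergent, contrary to the protocol's started-or-worsened definition

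*SAP*

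**What the plan says.** **SAP rule.** Section 2.1.1 of the primary-analysis SAP says that AE tables "will summarize only on-treatment events, with a start date during the on-treatment period" and labels these events treatment-emergent. The on-treatment period runs "from date of first administration of study treatment to 30 days after date of last administration of eltrombopag". Section 2.8 repeats the rule, and the general reporting rules in 2.8.1 add that "AE summaries will include all AEs occurring during on treatment period". The final-analysis SAP carries the same text in 2.1.1, 2.8 and 2.8.1; for example, its section 2.8 reads "In particular, summary tables for AEs will summarize only on-treatment events, with a start date during the on-treatment period".

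**CRF rule.** Protocol 10.1.1 has AEs recorded from the signing of consent. When an event worsens, it is entered again with the date of worsening. When a Grade 3 or 4 event improves to a lower grade, "a new entry for this event should be reported in the CRF noting the start date when the event improved". Conditions already present at consent go to medical history instead.

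**Protocol definition.** Protocol 12.5.2 states that "Summary tables for AEs will include only AEs that started or worsened during the on-treatment period". It counts an event that predates treatment only if the event increased in severity, moved from not suspected to suspected of a drug relationship, or became serious after treatment start. The same section also contains the start-date sentence that the SAPs use.

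**The concern.** The SAPs select on a date, and the CRF gives an improving Grade 3-4 event a fresh date. The two rules together can turn a recovery into a treatment-emergent event: the condition arose before any study drug was given and then got better, yet its second entry starts inside the on-treatment window.

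Safety and tolerability is a stated secondary objective. The trial has a single arm of 36, so there is no control rate against which such misclassification would cancel. The error runs in one direction only, towards overcounting. It is also an undeclared departure from one of the protocol's wordings: section 4 of each SAP, which lists changes to protocol-specified analyses, does not mention it.

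**Working it through.** The plan states no figure that depends on this rule, so there is nothing to reproduce. The check is of selection logic, followed by the arithmetic of one participant.

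**Inputs**
- SAP rule: an entry is treatment-emergent if it starts on or after first study treatment, up to 30 days after the last eltrombopag dose (SAP 2.1.1).
- Protocol severity test: an entry is treatment-emergent if the event is new on treatment, or if its grade is above the last grade before dosing (Protocol 12.5.2). The suspected-relationship and seriousness conditions are assumed not to be triggered in these examples.
- Entry rules: Protocol 10.1.1, as above.
- Pre-treatment window: screening begins up to 30 days before treatment (Protocol 8.1).
- Denominator: 36 enrolled (Protocol, Amendment 3 rationale), assumed all treated.

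**Constructed event histories under both rules**

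| History | SAP rule | Protocol severity test |
|---|---|---|
| Grade 3 in screening, Grade 2 from Day 5 | counted, maximum Grade 2 | not counted |
| Grade 4 in screening, Grade 3 from Day 5 | counted, maximum Grade 3 | not counted |
| Grade 2 in screening, Grade 3 from Day 5 | counted, maximum Grade 3 | counted |
| New Grade 2 on Day 5 | counted, maximum Grade 2 | counted |
| Grade 2 in screening, later Grade 1 | no new entry, not counted | not counted |
| Grade 3 improving to Grade 2 before dosing, then stable | not counted | not counted |
| Grade 3 in screening, Grade 2 from Day 5, Grade 3 again from Day 20 | counted, maximum Grade 3 | not counted, because the grade never exceeds the pre-dose grade |

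The rules agree on genuine worsening and on new events. They part in the first two rows, where the only post-dose change is an improvement. They also part in the last row, where the answer depends on taking the pre-dose entry as the comparator.

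**Whether another SAP rule removes the entry**
- Counting a participant once per category, and taking the maximum grade (2.8.1), both act within the on-treatment tables. The original entry starts before Day 1 and lies outside them, so the improvement entry stands alone.
- The first-episode onset rule (2.8.1) applies to the by-period table of AEs already classed as on-treatment.
- Neither SAP links entries of one event or compares an entry with the pre-dose grade.

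**Size per participant**
- One participant: 1/36 = 2.8 percentage points on a term, at most.
- Illustration only, assuming two or three participants share the same term: 2/36 = 5.6 and 3/36 = 8.3 points.
- If the participant has the same preferred term on treatment for another reason, the addition to that term's incidence is 0.
- The Grade 3 or higher table is affected by improvement alone only in the Grade 4 to Grade 3 case.

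**The case against.** The best defence is that the SAPs speak of events with a start date, not of CRF entries, and Protocol 10.1.1 describes the improvement as an entry for the same event. Both SAPs say they are based on protocol version 03. On that reading an event that began before Day 1 did not start on treatment, and the gap is only an unwritten derivation step. The reading is possible, but neither SAP states it, and a programmer working from CRF start dates would not arrive at it.

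It is also fair to say that the SAPs did not invent the rule, because Protocol 12.5.2 contains the start-date sentence. A reader might infer that the SAPs overrode a clear protocol definition. The documents do not support that: the protocol holds two wordings and the SAPs kept only one.

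The limits on scope stand. An affected event must begin after consent and before first dose, be Grade 3 or 4 at dosing, and then step down; resolution is recorded as an outcome and opens no new entry. Eligibility is checked at Screening and on Day 1. Protocol 5.2 excludes active uncontrolled significant infection, AST or ALT above 3 times ULN, creatinine at or above 2.5 times ULN, and active skin, mucosal, ocular or GI disorders above Grade 1. Overcounting is conservative for a safety claim, and the listings show every entry with pre-treatment ones flagged. These points reduce the size of the problem but do not make the selection rule agree with the started-or-worsened definition.

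**Conclusion.** The point holds as a conflict of rules with a probably small effect. As written, both SAPs classify the improvement of a pre-dose Grade 3-4 event as treatment-emergent, and the protocol's started-or-worsened definition does not.

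The number affected cannot be derived from the documents. The effect is at most 2.8 points per participant on a given term, assuming a denominator of 36 and no other on-treatment occurrence of that term. It could extend to the drug-related, serious and special-interest AE tables if those attributes are copied to the new entry.

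A reader might go further and infer that infection or cytopenia-complication rates are materially inflated, or that several participants are misclassified. The documents give no screening-period AE rate and no sign that the affected events concentrate in those terms, and the eligibility criteria remove some of the likeliest candidates. Nor is there a basis for saying that Grade 3 or higher rates are generally inflated, since most step-downs from Grade 3 leave that table untouched.

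**What to change.** In sections 2.1.1 and 2.8 of both SAPs, apply the protocol's definition in place of the bare start-date rule, and say that the start-date sentence is to be read subject to it. An entry opened because an event that began before first study treatment has improved is not treatment-emergent unless, compared with its pre-dose entry, the event increased in severity, changed to a suspected relationship or became serious after treatment start. Keeping these three exceptions matters: excluding every lower-grade continuation would drop events that the protocol intends to count.

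To identify such entries, link a Grade 3-4 entry to the lower-grade entry of the same preferred term that starts when the first one ends. Entries that are not contiguous in this way are separate episodes and stay counted. All entries remain in the listings.

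The cost is a short text change and one derivation step. A few AE percentages may fall.
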